9.2 Research Biopsies

Patients will undergo research biopsies of accessible primary tumor or a pathologic lymph node at up to 3 timepoints during protocol treatment:

1) Baseline research biopsy will occur after documentation of eligibility, and prior to initiation of protocol treatment. All efforts will be made to couple the baseline research biopsy to a standard of care procedure. NOTE: Patients who have had research tissue procured under an omnibus tissue consent, who are determined to have sufficient fresh, fresh-frozen, and paraffin tissue for analysis of immune-inflammatory biomarkers per the PI, may substitute the archived tissue and do not need to undergo baseline research biopsy.

2) Patients will be asked to undergo an optional second research biopsy at the second week of cisplatin-IMRT.

3) Patients will be asked to undergo another optional research biopsy at the second week of Pembrolizumab.

NOTE: All effort should be made to biopsy the same site originally biopsied (i.e. primary tumor or pathologic lymph node), if accessible. The research biopsy will occur either in the outpatient office of the otolaryngologist/head and neck surgeon, or in the interventional radiology suite of the radiologist. Imaging guidance with ultrasound or CT may be used as necessary. Local anesthetic will be administered per standard of care.

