9.4.5 Whole Exome Sequencing and RNA-Seq Analysis

To define the neo-epitope landscape and to delineate alterations in transcriptomic signatures we will complete whole exome sequencing (WES) and RNA-Seq on all protocol patients. WES will be performed on baseline tumor samples and DNA from corresponding peripheral blood samples. Somatic mutations and candidate neo-antigens generated from these mutations will be characterized. Neo-antigen prediction will be performed using HLA binding algorithms.^{43,44} RNA-Seq analysis will be performed in matched baseline and Week 2 of CRT biopsies, so the patient's baseline tissue serves as his/her own control. The goal of these studies is to describe the baseline mutational burden and neo-epitope landscape, and to identify changes in RNA-Seq defined transcriptomic signatures. Associations with clinical response and PFS will be evaluated. In particular, RNA-Seq data will highlight which of the predicted neo-epitopes are expressed during CRT alone as compared to patients treated with CRT and concurrent pembrolizumab. These data will describe the immunomodulatory role of CRT distinct from the addition of pembrolizumab and will provide powerful biomarker insight into the potential value of concurrent vs. sequential treatment.

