9.4.6 Paired Analysis of TCR Clonality in Pre- and Post-Treatment Tumor Specimens

To define the alterations in TCR clonality between matched baseline and Week 2 CRT biopsies from this trial, we will use the ImmunoSeq assay from Adaptive Biotechnologies to sequence TCR beta chains (as performed previously by the [name] laboratory). The goal of these studies is to examine oligoclonal expansion of T cell subsets and correlate these with clinical outcomes. Clonotypic expansion is a biomarker for a tumor-specific immune response in the absence of knowing tumor antigens of interest a priori.

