To define the neoepitope landscape and to delineate alterations in transcriptomic signature, we will complete whole exome sequencing (WES) and RNA-Seq on all 45 patients who receive pembrolizumab. Fisher's Exact test will be used to compare mutational burdens and differences in the frequency of nucleotide changes. Differentially

expressed genes will be identified and differences between treatment groups and clinical response groups will be explored. Log-rank tests will be used to compare Kaplan-Meier curves, and the relationship with PFS will be further characterized by proportional hazards (Cox) regression.

To define the alterations in TCR clonality between matched baseline and Week 2 CRT biopsies from this trial, we will use the ImmunoSeq assay from Adaptive Biotechnologies to sequence TCR beta chains. Differences in TCR clonality between treatment groups and clinical response groups will be explored using Fisher exact test.

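### Fisher's exact test is named for TCR clonality and mutational burden without any categories, and Section 10.4 names no test specifically for the within-patient change in clonality

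*Combined protocol and SAP*

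**What the plan says.** The test for clonality in Section 10.4 is "Differences in TCR clonality between treatment groups and clinical response groups will be explored using Fisher exact test". For the exome data the same section says "Fisher's Exact test will be used to compare mutational burdens and differences in the frequency of nucleotide changes". That sentence does not name the groups to be compared.

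The clonality data are matched within patient. Section 9.4.6, whose title calls the analysis paired, begins "To define the alterations in TCR clonality between matched baseline and Week 2 CRT biopsies from this trial", and Section 10.4 repeats this. Section 9.4.6 adds "The goal of these studies is to examine oligoclonal expansion of T cell subsets and correlate these with clinical outcomes". The exome data are not paired over time, because Section 9.4.5 says "WES will be performed on baseline tumor samples and DNA from corresponding peripheral blood samples".

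Exome and RNA sequencing are planned "on all 45 patients who receive pembrolizumab". The number of matched TCR pairs is not stated. Section 9.2 makes the second biopsy voluntary: "Patients will be asked to undergo an optional second research biopsy at the second week of cisplatin-IMRT".

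Elsewhere in Section 10.4, item 2 assigns a Wilcoxon test to paired pre/post immune and inflammatory markers. The opening of Section 10 describes a single-arm phase 2 trial.

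**The concern.** Fisher's exact test works on a table of counts in categories. Neither clonality nor mutational burden comes in categories, and Sections 9.4.5, 9.4.6 and 10.4 define none. As written, the analysis cannot be run until someone picks a cut, and nothing prevents that choice from being made with the data in view.

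Three things follow. Splitting a continuous measure throws away information, in a trial with at most a few dozen evaluable biopsies. The result comes to depend on the cut. And the stated aim of describing change between matched biopsies has no test clearly attached to it, since the only one named for clonality is a comparison between groups. Part of that comparison, between treatment groups, has no data behind it in a single-arm trial.

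**Working it through.** **No figure to reproduce.** The documents give no power, alpha, effect size or cut for these analyses. Everything below rests on assumptions, with ranges shown.

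**Inputs.**
- From the documents: 45 patients (Section 10.4), used as a working maximum; one arm (Section 10).
- Assumed: normally distributed values; standardised difference 0.5 to 1.0 SD; response groups of 22/23, 16/29, 9/36 or 10/35; two-sided 5%; Fisher applied to a split at the pooled median.

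**Method.** Power is the share of simulated data sets with p < 0.05. The rank-sum p-value uses the normal approximation to the Mann-Whitney statistic. The Fisher p-value is the two-sided hypergeometric probability for the 2×2 table of group by above or below the cut. With 45 patients the median is one patient's own value, so that patient can be counted in the upper or the lower half. Both choices were run. Results carry simulation error of about one point.

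| Split | Difference (SD) | Rank-sum | Fisher, better placing | Fisher, worse placing |
|---|---|---|---|---|
| 22/23 | 0.5 | 36% | 27% | 18% |
| 22/23 | 0.8 | 72% | 57% | 45% |
| 16/29 | 0.8 | 68% | 47% | 39% |
| 9/36 | 0.5 | 24% | 11% | 10% |
| 9/36 | 0.8 | 52% | 29% | 24% |
| 10/35 | 1.0 | 73% | 61% | 34% |

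**Loss at 0.8 SD.**
- 22/23: 72 − 57 = 15 points (15/72 = 21% of the rank-sum power) to 72 − 45 = 27 points (27/72 = 38%).
- 9/36: 52 − 29 = 23 points (23/52 = 44%) to 52 − 24 = 28 points (28/52 = 54%).

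Across differences of 0.5 to 1.0 SD and all four splits, the loss runs from about 4 to about 39 points. The low end is 25% against 21% (10/35, 0.5 SD, better placing). The high end is 73% against 34% (10/35, 1.0 SD, worse placing).

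**Dependence on the cut.**
- The last table row shows it directly: moving one patient across the median changes power from 61% to 34%.
- With groups of 35 and 10 and a 0.8 SD difference, a lower-tertile, a median and an upper-tertile cut disagreed on significance in 33% to 42% of simulated data sets, depending on which group had the higher values.
- With no true difference (22/23), accepting any significant result from five cuts gave about 11% false positives (9% to 12% depending on the five chosen) against a nominal 5%.

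**Within-patient change.** Sections 9.4.6 and 10.4 both state the matched-biopsy aim. The sentence that does so in Section 10.4 names a sequencing assay, and the only test that follows is the between-group Fisher test.

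**The case against.** A reader might infer that Fisher's test will compare baseline with Week 2 clonality and so discard the pairing. The documents do not say this. The sentence assigns the test to comparisons between groups of different patients, who are independent. If each patient's change were classed as expansion or no expansion, Fisher across response groups would even keep the pairing. An unpaired Fisher test of baseline against Week 2 would be poor: at a 0.5 SD shift and correlation 0.5, power is 8% against 40% for signed-rank with 15 pairs, and 39% against 90% with 45. Those figures describe a misuse that the plan does not propose.

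Nor is mutational burden paired. Exome sequencing uses baseline tumour, with blood DNA as the corresponding sample.

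It is also tempting to say that most of the power is lost. For the stated comparison this holds only in some unbalanced splits. In the balanced split at 0.8 SD the loss is a fifth to two fifths.

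Two further points carry weight. Fisher's test is acceptable for frequencies of nucleotide changes, which share the sentence with mutational burden. And item 2 of Section 10.4 could be read broadly enough to cover paired clonality, since Section 1.8 lists TCR clonality among the paired correlative studies. That makes the gap one of clarity rather than contradiction. Finally, the work is labelled exploratory. None of this supplies the missing categories.

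**Conclusion.** The point holds as a minor one. Fisher's exact test is the wrong default for clonality and mutational burden, because it needs categories that the plan does not define. Under the assumptions above, a median split costs a substantial part of the power: at 0.8 SD, roughly 15 to 27 points with balanced groups and 23 to 28 points with a 9/36 split. The result also depends on where the cut falls.

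These sizes rest on assumed normal data, effect sizes, response splits and 45 evaluable patients. Fewer will have matched biopsies if uptake of the optional Week 2 sample is incomplete. The absence of categories, the lack of an explicit test for within-patient change, and the reference to treatment groups in a one-arm trial need no assumptions. The primary PFS test, the sample size and the safety monitoring are untouched.

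**What to change.** In Section 10.4:

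1. Compare clonality (baseline value and baseline-to-Week 2 change) and mutational burden between clinical response groups with the Wilcoxon rank-sum test.
2. Test within-patient change in clonality with the Wilcoxon signed-rank test, in line with item 2's use of a Wilcoxon test for other paired markers, and report the number of matched pairs.
3. Keep Fisher's exact test for truly categorical data, such as presence or absence of a given mutation or nucleotide-change frequencies.
4. Delete the comparison between treatment groups, both in the clonality sentence and in the sentence on differentially expressed genes.

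The cost is rewording a few sentences, with no new data and no change in sample size. It should be done before the sequencing data are examined, so that no cut is chosen afterwards.

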10.5 Bayesian Continuous Monitoring for Futility

We will continuously monitor PFS data for futility. Under the null hypothesis of no improvement in PFS due to the combination of pembrolizumab and ISA1-1b, the expected 2-year PFS is assumed to be 65%. Under the alternate hypothesis, PFS would improve to 75%. Assuming an exponential distribution, 65% PFS at two years is equivalent to an annual hazard rate of .215. To monitor efficacy, we will use Bayesian monitoring. We have selected a conjugate prior distribution for the annual hazard rate that has a Gamma distribution with a shape parameter of 4 and a rate of 18.6. This provides a mean of .215 and 80% confidence limits of (.09 - .36), equivalent to a 2 year PFS between 49 and 83%. We will close the trial for futility if there is low probability that the combination therapy will be effective. Specifically, if the posterior probability that the 2-year progression-free survival is greater than 65%, is less than 10%, the trial will be closed for futility. Monitoring and updating the posterior probability can occur at any time at the discretion of the investigator, either at regular intervals or as each patient completes follow-up.

11. LABELING, PACKAGING, STORAGE, AND RETURN OF CLINICAL SUPPLIES

11.1 Investigational Products

The investigator shall take responsibility for and shall take all steps to maintain appropriate records and ensure appropriate supply, storage, handling, distribution and usage of the investigational product, pembrolizumab, in accordance with the protocol and any applicable laws and regulations.

Clinical Supplies will be provided by Merck as summarized in Table

7. Table 12. Product Descriptions

Product Name & Potency	Dosage Form
Pembrolizumab 50 mg	Lyophilized Powder for Injection
Pembrolizumab 100 mg/ 4mL	Solution for Injection

Product Name & Potency	Dosage Form
ISA101b	Sterile Lyophilized Powder for Subcutaneous Injection after reconstitution (-20°C and in a secure location)

11.2 Packaging and Labeling Information

Clinical supplies will be affixed with a clinical label in accordance with regulatory requirements.

11.3 Clinical Supplies Disclosure

This trial is open-label; therefore, the subject, the trial site personnel, the Sponsor and/or designee are not blinded to treatment. Drug identity (name, strength) is included in the label text; random code/disclosure envelopes or lists are not provided.

11.4 Storage and Handling Requirements

Clinical supplies must be stored in a secure, limited-access location under the storage conditions specified on the label.

Receipt and dispensing of trial medication must be recorded by an authorized person at the trial site.

Clinical supplies may not be used for any purpose other than that stated in the protocol.

11.5 Storage and Handling Requirements

The investigator or designee is responsible for keeping accurate records of the clinical supplies received from Merck and ISA, the amount dispensed to and returned by the subjects and the amount remaining at the conclusion of the trial.

Upon completion or termination of the study, all unused and/or partially used investigational product will be destroyed at the site per institutional policy. It is the Investigator's responsibility to arrange for disposal of all empty containers, provided that procedures for proper disposal have been established according to applicable federal, state, local and institutional guidelines and procedures, and provided that appropriate records of disposal are kept.

12. ASSESSING AND REPORTING ADVERSE EVENTS

12.1 Definition of Adverse Event

Adverse event means any untoward medical occurrence associated with the use of the drug in humans, whether or not considered drug related.

Suspected adverse reaction. Any adverse event for which there is a reasonable possibility that the drug caused the adverse event (considered "possibly related"). For the purposes of safety reporting, "reasonable possibility" means there is evidence to suggest a causal relationship between the drug and the adverse event. Suspected adverse reaction implies a lesser degree of certainty about causality than adverse reaction, which means any adverse event caused by a drug.

Adverse reaction means any adverse event caused by a drug. Adverse reactions are a subset of suspected adverse reactions where there is reason to conclude that the drug caused the event.

Serious Adverse Event: Any untoward medical occurrence associated with the use of a drug in humans, whether or not considered drug related. Specifically, results in death, is life-threatening, requires inpatient hospitalization or causes prolongation of existing hospitalization, results in persistent or significant disability/incapacity, is a congenital anomaly/birth defect, or is an important medical event (defined as a medical event(s) that may not be immediately life-threatening or result in death or hospitalization but, based upon appropriate medical and scientific judgment, may jeopardize the subject or may require intervention [e.g., medical, surgical] to prevent one of the other serious outcomes listed in the definition above.) Any subject death within 30 days of the last dose of study drug, regardless of the causality or a secondary malignancy should also be recorded as a serious adverse event.

Life-threatening, suspected adverse reaction. A suspected adverse reaction is considered "life-threatening" if, in the view of either the Investigator (i.e., the study site principal investigator), its occurrence places the patient or

research subject at immediate risk of death. It does not include a suspected adverse reaction that had it occurred in a more severe form, might have caused death.

Unexpected, suspected adverse reaction. A suspected adverse reaction is considered “unexpected” if it is not listed in the general investigational plan or clinical protocol; or is not listed at the specificity or severity that has been previously observed and/or specified. If an investigator brochure is not required or available, suspected adverse reaction is not consistent with the risk information described in the general investigational plan or elsewhere in the current application, as amended. “Unexpected,” as used in this definition, also refers to adverse events or suspected adverse reactions that are mentioned in the investigator brochure as occurring with a class of drugs or as anticipated from the pharmacological properties of the drug, but are not specifically mentioned as occurring with the particular drug under investigation. Any clinically important increase in the rate of a serious suspected adverse reaction over that listed in the protocol or investigator brochure can also be considered unexpected. An aggregate analysis of specific events observed in a clinical trial (such as known consequences of the underlying disease or condition under investigation or other events that commonly occur in the study population independent of drug therapy) that indicates those events occur more frequently in the drug treatment group than in a concurrent or historical control group.

All observed or volunteered adverse events (serious or non-serious) and abnormal test findings, regardless of study group or suspected causal relationship to the study drug(s) will be recorded in the subjects’ case histories. For all adverse events, sufficient information will be pursued and/or obtained so as to permit 1) an adequate determination of the outcome of the event (i.e., whether the event should be classified as a serious adverse event) and; 2) an assessment of the causal relationship between the adverse event and the study drug(s). All toxicities encountered during the study will be evaluated on an ongoing basis according to the NCI Common Toxicity Criteria version 5.0.

Adverse events or abnormal test findings felt to be associated with the study drug(s) will be followed until the event (or its sequelae) or the abnormal test finding resolves or stabilizes at a level acceptable to the Principal Investigator.

In the event of an adverse event the first concern will be for the safety of the subject.

12.2 Review of Safety Information

The principal investigator/sponsor must promptly review all information **relevant to the safety of the drug obtained or otherwise received from foreign or domestic sources, including information derived from any clinical or epidemiological investigations, animal or in vitro studies, reports in the scientific literature, and unpublished scientific papers, as well as reports from foreign regulatory authorities and reports of foreign commercial marketing experience for drugs that are not marketed in the United States. The study sponsor must notify all participating investigators of potential serious risks, from clinical trials or any other source, as soon as possible. Definition of an Overdose for This Protocol and Reporting of Overdose to the Sponsor, to Merck and to ISA.**

For purposes of this trial, an overdose of pembrolizumab will be defined as any dose of 1,000 mg or greater (≥ 5 times the indicated dose). No specific information is available on the treatment of overdose of pembrolizumab. Appropriate supportive treatment should be provided if clinically indicated. In the event of overdose, the subject should be observed closely for signs of toxicity. Appropriate supportive treatment should be provided if clinically indicated.

For purposes of this trial, an overdose of ISA101b will be defined as any dose of 1000 mcg per peptide or greater (≥ 5 times the indicated dose). No specific information is available on the treatment of overdose of ISA101b. Appropriate supportive treatment should be provided if clinically indicated. In the event of overdose, the subject should be observed closely for signs of toxicity. Appropriate supportive treatment should be provided if clinically indicated.

indicated.

If an adverse event(s) is associated with (“results from”) the overdose of pembrolizumab or ISA101b, the adverse event(s) is reported as a serious adverse event, even if no other seriousness criteria are met.

If a dose of pembrolizumab or ISA101b meeting the protocol definition of overdose is administered without any associated clinical symptoms or abnormal laboratory results, the overdose is reported as a non-serious Event of Clinical Interest (ECI), using the terminology “accidental or intentional overdose without adverse effect.”

All reports of overdose of pembrolizumab with and without an adverse event must be reported within 24 hours to the Sponsor and within 2 working days to Merck Global Safety (Attn: Worldwide Product Safety; [contact]) using the departmental SAE form or on a Form FDA 3500 MedWatch.

All reports of overdose of ISA101b with and without an adverse event must be reported within 24 hours to the Sponsor and within 2 working days to the ISA contact: [contact] , [name] using the departmental SAE form or on a Form FDA 3500 MedWatch.

12.3 Reporting of Pregnancy and Lactation to the Sponsor, to ISA, and to Merck

Although pregnancy and lactation are not considered adverse events, it is the responsibility of investigators or their designees to report any pregnancy or lactation in a subject (spontaneously reported to them), including the pregnancy of a male subject's female partner that occurs during the trial or within 120 days of completing the trial completing the trial, or 30 days following cessation of treatment if the subject initiates new anticancer therapy, whichever is earlier. All subjects and female partners of male subjects who become pregnant must be followed to the completion/termination of the pregnancy. Pregnancy outcomes of spontaneous abortion, missed abortion, benign hydatidiform mole, blighted ovum, fetal death, intrauterine death, miscarriage and stillbirth must be reported as serious events (Important Medical Events). If the pregnancy continues to term, the outcome (health of infant) must also be reported.

Such events must be reported within 24 hours to the Sponsor and within 2 working days to **the Merck Global Safety [contact]**

AND

to the ISA contact: [contact] , [name].

using the departmental SAE form or on a Form FDA 3500

MedWatch.

12.4 Immediate Reporting of Adverse Events to the Sponsor, Institutional IRB, to ISA and to Merck

